14.2 Demographic and Baseline Characteristics

The following demographic variables at screening will be summarized: race, gender, age, duration of ADLD.

14.3 Analysis of Primary Endpoint

Our primary outcome is the difference in VHI-10 score at 8 weeks after injection with DAXI. This will be determined using a paired t-test with subjects pre-treatment VHI-10 scores as a control. Our second primary outcome measure is the duration of effect of DAXI, assessed qualitatively through phone calls, compared to patients' prior Botox treatment. We will produce a Kaplan-Meier curve to illustrate the duration of clinical benefit after treatment with DAXI.

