EFFICACY EVALUATIONS	Validated laryngology PROMs, voice analysis via mobile app (voice recording sample), duration of effect
PRIMARY ENDPOINT	Efficacy, measured quantitatively through VHI-10 questionnaires
SECONDARY ENDPOINTS	Duration of benefit, assessed qualitatively through phone call surveys
OTHER EVALUATIONS	Participant Questionnaires CPIB-10 OMNI-VES EAT-10

	Clinician Scales Unified spasmodic dysphonia rating scale (USDRS) Phonalyze
SAFETY EVALUATIONS	Incidence of adverse events
PLANNED INTERIM ANALYSES	When approximately 50% of patients have completed the study's initial injection, an interim analysis for safety will be conducted.
STATISTICS Primary Analysis Plan	Safety profile including AE and SAEs will be reported. Simple descriptive statistics will be used to summarize toxicities in terms of type, severity and minimum or maximum values for laboratory measures, time of onset, duration, and reversibility or outcome. Tables will be created to summarize these toxicities and side effects. Safety Analyses will be performed on Safety Analysis Set.
Rationale for Number of Subjects	A sample size of 20 will provide 80% power to detect a difference of 6.6 at a significance threshold (alpha) of 0.05.

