5.2 Secondary Efficacy Endpoints

The secondary endpoint is duration of benefit, assessed by median time to baseline VHI-10 after treatment with DAXI and via phone call surveys. VHI-10 questionnaires will be given at baseline, day 14, then monthly until loss of benefit. Phone calls will be conducted at day 5, day 14, then monthly until loss of benefit.

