7.2 Blinding

N/A (open-label study).

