9.5 Visit 4 (Phone call, Day 14*)

1. Phone call to assess clinical improvement
2. Ensure there is absence of dysphagia (using EAT-10 questionnaire), no injection site issue, or other adverse event

*Day 14 after most recent DAXI injection

9.6 Visits 5-10 (Remote Survey, every month starting 1 month after most recent injection)

1. Phone call to assess duration of benefit
2. Patient fills out PROMs electronically through Qualtrics to assess our primary (VHI-10) and secondary outcome measures

- VHI-10
 - CPIB-10
 - OMNI-VES
 - EAT-10
3. Patient records their voice in Phonalyze for CPP and CAPE-V analysis
 4. Patient will record whether DAXI still has desired effect

Data is collected monthly until loss of benefit.

For every instance when all PROMs and Phonalyze recordings are completed, patients will be paid \$10, up to \$150. After the completion of the study the number of entries will be tabulated and patient will be given a Visa gift card in the allotted amount. Patients who withdraw from the study will still be compensated for all instances when PROMs and Phonalyze recordings were completed.

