13 DATA SAFETY MONITORING

A Data Monitoring Committee (DMC) to review data relating to safety and efficacy, to conduct and review interim analyses, and to ensure the continued scientific validity and merit of the study, according to the UCSF IRB. The DMC will be made up of the investigator team (PI, other study clinicians, and research assistants) will be meeting at least every 2 weeks to review preliminary data. At this time, the following will be reviewed:

- Enrollment (number of participants)

- Adverse events
- Any unexpected voice/swallow/breathing problems based on the survey data collected
- Any phone calls by participants to the Voice and Swallowing Center
- Breaches of confidentiality
- Unanticipated problems

This information will be shared with the UCSF IRB every 6 weeks. If there are any adverse events or unanticipated problems, this will be communicated immediately. An interim analysis will be conducted and reported three months after the study start date, or after the 10th subject is recruited, whichever comes first. Any participants whose confidentiality has been breached will be notified as soon as possible.

A study subject's participation in the trial will be withdrawn immediately for any the following criteria:

- The patient wishes to end participation
- The patient undergoes an additional laryngeal Botox injection (at UCSF or elsewhere)
 - Unrelated medical event/condition which impacts voice/swallowing
- The trial will be halted immediately for any of the following events:
 - If a pattern of poor clinical outcomes is seen
 - For multiple adverse events
 - At UCSF IRB discretion

Based on UCSF IRB guidelines, this trial does not meet criteria for a Data Safety Monitoring Board, although one would be assembled if requested by the UCSF IRB. The study has none of the following features:

- There is a significant likelihood of a serious adverse event to participants
- The study is conducted at multiple sites and the level of risk is greater than minimal
- The study generates data that are blinded or randomized
- The study involves a large number of patients randomized to one of two or more interventions

- A study for which the performance of an interim analysis is crucial for the protection of the participants
- First use in humans
- First use in children
- The study involves gene therapy, stem cell therapy, or other novel interventions for which long-term outcome data are not known or available

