14.4 Analysis of Secondary Endpoints

A secondary outcome will be comparing the duration of effect of DAXI with patients' prior Botox treatment. Specifically, we will determine the median time to baseline VHI-10 after treatment with DAXI and produce a Kaplan-Meier curve to illustrate the duration of clinical benefit.

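### Duration of DAXI benefit is read from an unscripted, unmasked phone call listed ahead of the patient's own forms, while the patient's own record of benefit goes unused and the sections disagree on the source

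*Combined protocol and SAP*

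**What the plan says.** **Source of duration.** Four places define it, and they differ.

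- Synopsis, secondary endpoints: "Duration of benefit, assessed qualitatively through phone call surveys".
- Section 5.2: "assessed by median time to baseline VHI-10 after treatment with DAXI and via phone call surveys".
- Section 14.3, where duration is called a second primary outcome and set against prior Botox: "duration of effect of DAXI, assessed qualitatively through phone calls".
- Section 14.4, for the comparison with prior Botox: "we will determine the median time to baseline VHI-10 after treatment with DAXI".

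**Monthly contact.** Section 9.6 (Visits 5-10) has four numbered items. Item 1 is "Phone call to assess duration of benefit". Item 2 is the set of questionnaires the patient completes in Qualtrics, including VHI-10. Item 3 is the voice recording. Item 4 is "Patient will record whether DAXI still has desired effect". Appendix 1 has a row for the call and none for item 4.

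**Setting.** Section 7.2 gives blinding as not applicable because the study is open-label. Sections 2 and 3.2 state the aim of learning whether DAXI lasts longer than BotoxA. Under section 9.1, prior Botox treatments are taken as medical history at phone screening.

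**The concern.** Whether benefit has gone is a soft judgement for a patient close to the threshold. If the answer is given in conversation with someone who knows the treatment and may hope for a longer effect, a borderline reply can slip to the next monthly contact. Only the DAXI period is followed by repeated calls. Prior Botox duration comes from history, so any effect of the calls does not cancel in the comparison, and no concurrent arm would reveal it.

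Two further consequences are possible. If the call is made before the forms, a conversation about whether DAXI is still working precedes the self-completed VHI-10, including the one used for the 8-week primary endpoint. And sections 5.2 and 9.6 collect VHI-10 monthly until loss of benefit, which is not defined. If the call decides that moment, it also decides when VHI-10 collection stops, and time to baseline VHI-10 is then not an independent check.

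The exposure is avoidable, because the same contact already asks the patient to record the answer.

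**Working it through.** **1. What the text settles and leaves open**

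| Question | Documents |
|---|---|
| Source of duration | Call (synopsis, 14.3); VHI-10 and call (5.2); VHI-10 (14.4) |
| Who places the calls | Not stated |
| Script, or definition of loss of benefit | Not given |
| Forms required before the call | No; the call is item 1 and the forms item 2, but the order is not stated to be mandatory |
| How item 4 is captured | Not stated; it is not among the Qualtrics instruments listed under item 2 |
| Use of item 4 in the analysis | None in 14.3 or 14.4 |
| Rule if the sources disagree | None |

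**2. Reproducing the plan's duration figure**

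Inputs from section 14.6: SD 7.2 weeks, within-subject correlation 0.875, n = 20, difference 2.4 weeks, power 80%. Two-sided alpha of 0.05 is an assumption: section 14.6 gives 0.05 in its VHI-10 sentence without saying whether it is two-sided.

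- SD of the difference = 7.2 × √(2 × (1 − 0.875)) = 7.2 × 0.5 = 3.6 weeks.
- Paired t-test with 19 degrees of freedom, non-centrality (2.4 / 3.6) × √20 = 2.98: power 80.7%, and 20 is the smallest n that reaches 80%.

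The stated figure reproduces. Sections 14.3 and 14.4 name only a median and a Kaplan-Meier curve for duration, so the paired t-test is inferred from this power statement.

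**3. How coarse one contact is against the target**

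- One month = 365.25 / 12 / 7 = 4.35 weeks.
- 2.4 / 4.35 = 0.55, so the planned difference is about half of one contact interval.

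**4. Illustration of a shift**

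Assumptions: true difference zero, SD of the difference 3.6 weeks, n = 20, two-sided 5% paired t-test, and a share f of subjects whose loss of benefit is recorded one contact (4.35 weeks) late. The values of f are not in the documents. Mean shift = f × 4.35. The false-positive rate in DAXI's favour is simulated.

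| f | Mean shift (weeks) | Share of 2.4 weeks | Significant in DAXI's favour |
|---|---|---|---|
| 0 | 0 | 0% | 2.5% |
| 10% | 0.43 | 18% | about 7% |
| 20% | 0.87 | 36% | about 14% |
| 30% | 1.30 | 54% | about 26% |

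**The case against.** **The call is not the only measure.** This stands. Section 5.2 adds time to baseline VHI-10, and section 14.4 uses it specifically for the comparison with prior Botox; VHI-10 is completed by the patient. It narrows the point without removing it. The call remains the source for the outcome that section 14.3 calls primary and the only source in the synopsis, and the plan does not rank the two.

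**Item 4 may not be an independent self-report.** This also stands. Section 9.6 does not say where the patient records the answer, and it could be taken during the call. A reader might infer that the plan already holds a clean self-completed answer and picks the worse source; the text does not go that far. The fix must therefore state how item 4 is captured.

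**A numbered list is not a sequence.** Correct. A reader might infer that the call always comes first and colours the primary VHI-10. The documents show only that it is listed first and that nothing protects the forms.

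**The caller and the bias are conjecture.** A reader might infer from section 13, where the investigator team reviews data at least every 2 weeks, that this team places the calls. The documents do not say so, and they mention other personnel: a trained preparer (7.4.3), site staff (7.6), study personnel (15.1) and a data management group (15.2). Nor do they establish the direction or size of any bias.

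**Larger problems remain after the fix.** True. The patient also knows the treatment, the comparator is still history, and the monthly grid is unchanged. If loss is dated at the contact that reports it and prior Botox duration is not rounded in the same way (both assumptions), rounding alone adds 4.35 / 2 = 2.17 weeks on average, more than the largest shift illustrated here. That is a reason to report these limitations, not to keep an avoidable one.

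**Conclusion.** The concern holds in limited form. In an open-label trial, the duration outcome in section 14.3 and the synopsis rests on a qualitative phone call with no script, no definition of loss of benefit and no required order relative to the forms. The patient's own record from the same contact is not analysed, and sections 5.2 and 14.4 name a different or additional source. Interviewer influence on duration, and possibly on VHI-10, is an avoidable risk. Longer apparent DAXI duration is its likely direction, because only the DAXI period is measured by calls and longer benefit is what the trial hopes to find, but this is not proven.

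The false-positive rates of about 7%, 14% and 26% are illustrations. They depend on assumed shares, a zero true difference and an inferred paired t-test. They show that a few borderline answers can matter when the target is about half a contact interval; they do not estimate the bias. No sample-size figure is wrong on this point. The change should be made; confidence is medium.

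**What to change.** 1. **Section 9.6.** Require the Qualtrics questionnaires and the item 4 answer to be submitted before the call. State that the patient enters item 4 in Qualtrics.
2. **Section 14.3, section 5.2 and the synopsis.** Replace the phone call as the source of duration with the patient's own recorded answer as the loss-of-benefit event. In section 5.2 the words to change are the reference to phone call surveys at the end of "assessed by median time to baseline VHI-10 after treatment with DAXI and via phone call surveys"; in the synopsis they are "Duration of benefit, assessed qualitatively through phone call surveys". Word the question as loss of benefit, because section 9.4 uses desired effect in another context, the optional second injection. Keep time to baseline VHI-10 as the separate measure in section 14.4.
3. **Role of the call.** Keep it for adverse events and for chasing missing forms. Use a call-based answer only as a flagged fallback, and report how often the call, the patient's record and time to baseline VHI-10 disagree.
4. **Reporting.** List the patient's open-label expectation, monthly rounding and the history-based comparator as remaining limitations.

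Cost: wording, a reordering of an existing contact, and one added Qualtrics question if item 4 is not there already. No visit is added, and the sample size is unchanged. The small downside is that some late forms will need the flagged fallback.

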14.4 Analysis of Secondary Endpoints

A secondary outcome will be comparing the duration of effect of DAXI with patients' prior Botox treatment. Specifically, we will determine the median time to baseline VHI-10 after treatment with DAXI and produce a Kaplan-Meier curve to illustrate the duration of clinical benefit.

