	
wear off and the sometimes challenging access to treatment, a longer acting agent is desire.
 
Injectable daxibotulinumtoxinA (DAXI, Revance Therapeutics Inc., Newark, CA) is a FDA-approved botulinum toxin type A indicated for the treatment of glabellar lines. It has been shown in large clinical trials to provide safe, effective treatment for cervical dystonia and may offer longer-lasting results when compared with onabotulinumtoxinA.
 
Thus, a study examining the effect of DAXI for patients with adductor laryngeal dystonia (ADLD) is proposed. This study aims to assess the efficacy of DAXI for transcervical laryngeal injection in patients with adductor laryngeal dystonia.

STUDY DESIGN	A single-arm, open-label, dose-escalation phase 4 study.
PRIMARY OBJECTIVE	Determine the efficacy of DAXI for treatment of ADLD.
SECONDARY OBJECTIVES	Compare duration of benefit between DAXI and BotoxA.
NUMBER OF SUBJECTS	20

SUBJECT SELECTION CRITERIA	
Inclusion Criteria:
 
Age ≥ 18
 
Diagnosis of adductor laryngeal dystonia (ADLD)
 
Previous successful treatment with BotoxA and stabilized dose for the last 3 treatments
 
Acceptable form of birth control for females of childbearing potential.
 
Women of childbearing age must have a negative pregnancy test
 
Female participants of childbearing potential may be enrolled in the study if the participant fulfills all the inclusion criteria listed in the subject selection section below.
 
Exclusion Criteria:
 
Age < 18
 
Other neurologic conditions (ALS, Parkinson's disease, essential tremor, Meige syndrome, etc.)
 
Pregnant, breastfeeding, or unwilling to practice birth control during participation in the study.
 
Presence of a condition or abnormality that in the opinion of the Investigator would compromise the safety of the patient or the quality of the data.
 
Naive from other types of Botox for 6 months including BotoxA

TEST PRODUCT, DOSE, AND ROUTE OF ADMINISTRATION	
Open-label dose of DAXI injected at either 0.625, 1.25, or 2.5 units. Dosage will be determined by subject's previous stabilized Botox dosage.

CONTROL PRODUCT, DOSE AND ROUTE OF ADMINISTRATION	N/A
DURATION OF SUBJECT PARTICIPATION AND DURATION OF STUDY	Subjects will be in the study for up to 36 weeks. Total time for recruitment and completion of the study will be up to 2 years.
CONCOMMITANT MEDICATIONS	Allowed: all Prohibited: Other forms of Botox

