3.2 Secondary Objectives

Determine duration of clinical benefit to assess whether DAXI may provide longer clinical benefit than BotoxA for treatment of ADLD

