9 EVALUATIONS BY VISIT

9.1 Phone Screening (7 Days prior to injection)

1. Confirmation participants meet all inclusion criteria and no exclusion criteria review
2. If they have provided consent to contact, reach out and explain the study to them.
3. Review the study with the subject (subject's legal representative) and obtain written informed consent and HIPAA authorization via DocuSign.
4. Assign the subject a unique screening number.
5. Record demographics data.
6. Record medical history, including history of ADLD, diagnosis date, and prior Botox treatments.
7. Patient fills out baseline PROMs electronically through Qualtrics (VHI-10, CPIB-10, OMNI-VES, EAT-10)
8. Patient records their voice in Phonalyze for CPP and CAPE-V analysis

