14.6 Sample Size and Randomization

One primary outcome is the difference in VHI-10 score at 6 weeks after injection with DAXI. The normative values of the VHI-10 have been established, with a normal value of 2.83 and standard deviation of 3.93. One prospective study for Botox in SD determined a pretreatment VHI-10 score of 22.58 +/- 7.09 and 6-week post-treatment 20.86 +/- 7.24. The difference had a standard deviation of approximately 10. A sample size of 20 will provide 80% power to detect a difference of 6.6 at a significance threshold (alpha) of 0.05.

A secondary outcome will be comparing the duration of effect of DAXI with patients' prior Botox treatment. Specifically, we will determine the median time to baseline VHI-10 after treatment with DAXI and produce a Kaplan-Meier curve to illustrate the duration of clinical benefit. A large retrospective study from Blitzer et al from described the average duration of benefit to be about 15.1 weeks with a standard deviation of 12.3 weeks [10]. Unpublished data from our institution revealed an average duration of 18.9 weeks with a standard deviation of 7.2 weeks. Using the data from our institution, a sample size of 20 will provide 80% power to detect a difference in average duration of 2.4 weeks. (This calculation assumed a with-subject correlation coefficient of 0.875.)

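### As written, the duration analysis cannot answer objective 3.2: it specifies only a DAXI median and curve, while the 2.4-week power figure belongs to a paired comparison with Botox that is not specified

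*Combined protocol and SAP*

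**What the plan says.** **Objective.** Section 3.2 sets out to "assess whether DAXI may provide longer clinical benefit than BotoxA for treatment of ADLD". The Protocol Synopsis puts it as "Compare duration of benefit between DAXI and BotoxA".

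**Endpoint.** Section 5.2 measures duration in two ways: time until VHI-10 returns to baseline, and phone surveys. The Synopsis gives only the second: "Duration of benefit, assessed qualitatively through phone call surveys".

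**Analysis.** Section 14.3 calls phone-assessed duration a second primary outcome, to be set against prior Botox treatment. It names no method beyond a Kaplan-Meier curve for DAXI. Section 14.4 treats duration as secondary, announces a comparison with prior Botox, and then makes it specific: "we will determine the median time to baseline VHI-10 after treatment with DAXI and produce a Kaplan-Meier curve". Section 14.6 repeats this.

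**Power.** Section 14.6 claims "80% power to detect a difference in average duration of 2.4 weeks" with 20 subjects, using the institution's own SD of 7.2 weeks. It adds: "This calculation assumed a with-subject correlation coefficient of 0.875".

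**Botox data.** The screening instruction in section 9.1 is "Record medical history, including history of ADLD, diagnosis date, and prior Botox treatments". Appendix 1 schedules VHI-10 at screening and after DAXI only.

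**The concern.** The objective is a contrast between two drugs, but the specified output describes one. A DAXI median and a DAXI curve contain no Botox term, no reference value and no test. The only hypothesis test named in section 14 is the paired t-test on VHI-10 at 8 weeks.

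The power statement refers to a different quantity: a difference in average duration with a within-subject correlation. That needs a Botox duration for each patient, and the plan does not say where it comes from, which prior cycles count, or how loss of benefit under Botox is defined.

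Followed literally, the trial would report a DAXI median and leave the choice of Botox benchmark until after the data are seen. The data gap is the more urgent part. An analysis can be added later, but durations not captured systematically at screening may not be recoverable.

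**Working it through.** **1. What each section supplies**

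| Section | Comparator named | Botox duration variable | Method for the comparison |
|---|---|---|---|
| 3.2, Synopsis | BotoxA | – | – |
| 9.1, Appendix 1 | – | none named; prior treatments recorded as history | – |
| 14.3 | prior Botox | none | none (DAXI curve only) |
| 14.4 | prior Botox | none | none (DAXI median and curve) |
| 14.6 | prior Botox | implied by the correlation | implied paired difference in means |

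**2. Reproducing the plan's figure**

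Inputs from 14.6: n = 20, SD 7.2 weeks, correlation r = 0.875, difference 2.4 weeks. Alpha 0.05 is stated there for VHI-10. I assume that it also applies to duration and is two-sided.

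- SD of the within-patient difference = 7.2 × √(2(1 − 0.875)) = 7.2 × 0.5 = 3.6 weeks.
- Standardised effect = 2.4 / 3.6 = 0.667.
- Paired t, 19 df, noncentral t: power 80.7%. The detectable difference at 80% power is 2.38 weeks.
- Alternatives fit less well: normal approximation 84.7%, one-sided t 89.0%.

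The arithmetic is therefore right, and it identifies the analysis assumed: a paired t-test on mean duration.

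**3. Dependence on the correlation**

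For n = 20 and 80% power, the detectable difference is 0.660 × the SD of the difference. Two estimators are shown:

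- DAXI minus one Botox cycle: SD of difference = 7.2 × √(2(1 − r)).
- DAXI minus the mean of 3 Botox cycles, assuming equal SDs and the same correlation r between any two cycles. The variance is 7.2² × [1 + (1 + 2r)/3 − 2r] = 7.2² × (4/3)(1 − r).

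| r | One cycle: SD of difference | Detectable (weeks) | Power for 2.4 | 3-cycle mean: SD of difference | Detectable (weeks) | Power for 2.4 |
|---|---|---|---|---|---|---|
| 0.875 | 3.60 | 2.4 | 81% | 2.94 | 1.9 | 93% |
| 0.8 | 4.55 | 3.0 | 61% | 3.72 | 2.5 | 78% |
| 0.7 | 5.58 | 3.7 | 45% | 4.55 | 3.0 | 61% |
| 0.5 | 7.20 | 4.8 | 29% | 5.88 | 3.9 | 41% |

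The documents give only r = 0.875, without a source. The lower values are illustrative. All rows assume a paired t-test without censoring.

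**4. What the specified median could show**

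For illustration, assume normal durations with SD 7.2, a true DAXI median of 18.9 + 2.4 = 21.3 weeks, and no censoring. In simulation, the order-statistic 95% interval for the median of 20 patients (6th to 15th values) runs on average from 17.1 to 25.6 weeks. It lies wholly above 18.9 in about 19% of trials, even if 18.9 is treated as a known constant. A DAXI-only median does not carry the 80% power quoted.

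**The case against.** **The strongest defence** is that prior Botox is named as comparator in 14.3, 14.4 and 14.6, and section 14 promises a detailed SAP before the final analysis. The last 3 injections must already be known for eligibility (5.6) and dose (7.4.1). A self-report measure is already planned: phone surveys in 5.2, and a monthly record in 9.6 of whether DAXI still has the desired effect. All of this stands, and it makes the repair small. It does not supply the Botox-side variable or a method, and a later SAP cannot restore durations that screening did not capture.

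**Stronger readings that the documents do not support:**

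- *That the trial holds no Botox data, or could never answer the question.* Prior treatments are recorded, and some patients come from the same centre, so records may exist. The gap lies in the analysis and the named variables as written.
- *That the paired comparison will never be run.* It is not specified; the promised SAP could add it.
- *That the power calculation is wrong.* It reproduces. Using the institution's SD of 7.2 rather than the published 12.3 is defensible for a single-centre trial.
- *That the gap between the two quoted Botox means (18.9 − 15.1 = 3.8 weeks) defeats the comparison.* The stated comparator is each patient's own prior treatment, so a gap between external means does not bear on it.
- *That Botox durations would necessarily be remembered, or measured on another scale.* The plan does not say how they would be obtained.

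**Conclusion.** The concern holds for the plan as written. Objective 3.2 has no specified analysis that addresses it, and the stated power belongs to a within-patient difference in mean duration that 14.3 and 14.4 do not contain. This is more than missing detail, because the Botox durations that such a comparison needs are not named for collection.

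The 80% for 2.4 weeks is correct on its own inputs but depends on r = 0.875. Against a single Botox cycle, power for 2.4 weeks falls to 45% at r = 0.7 and 29% at r = 0.5. A 3-cycle mean is more favourable (61% and 41%), provided SDs are equal and correlation is exchangeable. These figures assume two-sided 0.05, SD 7.2, and 20 complete pairs without censoring.

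**What to change.** 1. **Screening (9.1).** For each of the last 3 BotoxA treatments, record the injection date and when benefit was lost. Use clinic records where available and patient report otherwise, with the same loss-of-benefit question as in the DAXI calls.

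2. **Analysis (14.4, with 14.3 and 14.6 aligned).** Define the comparison as the within-patient difference in self-reported duration, DAXI minus the mean of the last 3 BotoxA cycles. Pre-specify one method that allows for DAXI durations censored at 36 weeks, such as a paired Prentice-Wilcoxon or sign test, and give an estimate with a 95% CI. Do not leave the choice of test until censoring has been seen. State one time origin for patients given a second DAXI injection, consistent with 9.6, which counts visits from the most recent injection. Keep the VHI-10 Kaplan-Meier curve as descriptive.

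3. **Power (14.6).** Restate the detectable difference for the estimator chosen, as a range over correlation: 2.4 to 4.8 weeks against one cycle, or 1.9 to 3.9 weeks against the 3-cycle mean, for r from 0.875 to 0.5. Give the source of 0.875 or label it an assumption. Note that a rank or sign test would be somewhat less favourable than these paired-t figures.

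**Cost.** A few screening questions and some rewording. Some Botox durations will be recalled while DAXI durations are recorded prospectively, which should be stated as a limitation. The single detectable difference becomes a range that is less favourable at lower correlations.

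### Duration is defined as time to baseline VHI-10, but VHI-10 collection stops at reported loss of benefit; with no event rule, the planned median can be too early or too late

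*Combined protocol and SAP*

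**What the plan says.** - **Event.** Section 14.4 sets the duration parameter as the "median time to baseline VHI-10 after treatment with DAXI", with a Kaplan-Meier curve. Section 14.6 repeats this definition. Section 5.2 names two measures together: "duration of benefit, assessed by median time to baseline VHI-10 after treatment with DAXI and via phone call surveys". No rule combines them.
- **Baseline.** Section 9.1 and Appendix 1 schedule one pre-treatment VHI-10, at screening.
- **End of VHI-10 sampling.** Section 5.2: "VHI-10 questionnaires will be given at baseline, day 14, then monthly until loss of benefit". Section 9.6 agrees: "Data is collected monthly until loss of benefit". So does Appendix 1. Section 5.1 has monthly VHI-10 without that stop. Loss of benefit is not defined. The item in 9.6 that bears on it is item 4: "Patient will record whether DAXI still has desired effect".
- **Second route to duration.** Section 14.3 makes duration assessed by phone call, compared with prior Botox, a second primary outcome, and plans a Kaplan-Meier curve. Section 14.4 treats duration as secondary, uses VHI-10, and also plans a curve.
- **Reference figures.** Section 14.6 cites mean durations of benefit of 15.1 weeks (SD 12.3) and 18.9 weeks (SD 7.2). For VHI-10 on Botox it cites a "pretreatment VHI-10 score of 22.58 +/- 7.09 and 6-week post-treatment 20.86 +/- 7.24", with an SD of the difference of about 10.
- **Re-injection.** Section 13 withdraws a subject who has another laryngeal Botox injection. No analysis rule follows.

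**The concern.** Two things can go wrong with a return-to-baseline event here. First, a fluctuating questionnaire score compared with a single baseline value can cross it while the drug is still working. Second, a subject who reports loss of benefit while VHI-10 is still a point or two below baseline gives no further scores. That subject has lost benefit but has no VHI-10 event, and the stopping is related to the outcome.

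Duration is the whole secondary objective in 3.2 and carries the comparison with BotoxA. The cited 15.1- and 18.9-week figures are durations of benefit, not times to VHI-10 return, and no VHI-10 series on prior Botox is scheduled. A median time to VHI-10 return therefore has nothing like-for-like to be set against.

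**Working it through.** **1. The plan's own figures (14.6), paired t-test, n = 20, two-sided alpha 0.05 (sidedness assumed).**
- VHI-10: 6.6/10 × √20 = 2.95, power 79.9%.
- Duration: SD of difference = 7.2 × √(2 × (1 − 0.875)) = 3.6; 2.4/3.6 × √20 = 2.98, power 80.7%.

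Both stated 80% figures reproduce. The second is for a paired difference in mean duration, not for a median time to a score threshold.

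**2. How much of SD 10 could be noise.** With SDs 7.09 and 7.24, SD of change = √(7.09² + 7.24² − 2r × 7.09 × 7.24). At r = 0 this is 10.13, so SD 10 implies almost no pre/post correlation. At assumed r of 0.5, 0.75 and 0.875 it is about 7.2, 5.1 and 3.6. The documents give no test-retest SD. I therefore used SDs of 10, 7, 5 and 3.6, with none or half of the variance being real differences in response.

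**3. One visit during benefit.** The chance of a score at or above baseline is Φ(−effect/SD).
- Powered effect 6.6: SD 10, 25%; SD 7, 17%; SD 5, 9%; SD 3.6, 3%.
- Cited BotoxA change 22.58 − 20.86 = 1.72, SD 10: 43%.

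**4. The planned median.** I simulated 200,000 subjects per row. Assumptions: true duration normal, 18.9 (SD 7.2) weeks; visits at week 2 and then six monthly visits (Visits 5–10, to about week 26); full effect until loss and none after; event at the first score at or above baseline; no more scores after the first contact following loss. Effect 6.6:

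| SD of change | Share that is real response difference | Cross before loss | Stop after loss, no event | Kaplan-Meier median (weeks) |
|---|---|---|---|---|
| 10 | 0 | 55% | 28% | 13.0 |
| 10 | 50% | 45% | 29% | 17.3 |
| 7 | 0 | 42% | 33% | 17.3 |
| 7 | 50% | 33% | 33% | 21.7 |
| 5 | 0 | 27% | 38% | 21.7 |
| 5 | 50% | 20% | 37% | 26.0 |
| 3.6 | 0 | 11% | 41% | 26.0 |
| 3.6 | 50% | 8.5% | 40% | 26.0 |

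Loss of benefit detected on the same grid has its median at 21.7 weeks: 59% are still in benefit at week 17.3 and 35% at week 21.7. The grid alone adds 21.7 − 18.9 = 2.8 weeks, more than the 2.4-week target.

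**5. Sensitivity.**
- At the cited effect of 1.72 with SD 10 to 5, the median is 4.3 to 8.7 weeks and 58 to 75% cross early.
- Rounding scores to whole numbers, so that ties count as a return, moves the first row from 13.0 to 8.7 weeks.
- In the 50% rows some early crossings are true non-response. At SD 10 the between-subject SD is 10 × √0.5 = 7.07, and Φ(−6.6/7.07) = 18% of subjects have no true improvement. At effect 1.72 the share is Φ(−1.72/7.07) = 40%.

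**The case against.** **First crossing is not in the plan.** This stands: the documents give no rule, and section 14 promises a SAP before the final analysis that could supply one. But a SAP cannot recover scores that were never collected after reported loss. Nor does confirmation alone rescue the measure. With whole-number scores, effect 6.6 and SD of change 3 to 10, requiring the return to be confirmed at the next visit left the median unreached by Visit 10, because sampling had already stopped in too many subjects.

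**SD 10 is not pure noise.** This stands. It contains real differences in response, so 25% and 43% are upper-end figures.

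**The 1.72-point effect may not fit this trial.** This also stands. Subjects must have had successful BotoxA treatment, a second injection is allowed, and the sample size rests on 6.6. The main result above therefore uses 6.6.

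**The different stopping criterion is an inference.** Partly right. Loss of benefit is undefined, and 5.1 omits the stop. The patient's own statement in 9.6 is the natural reading, not an explicit rule.

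**Stronger readings.** A reader might infer that noise rather than loss of effect triggers the event, so that the median is biased short. The documents do not support that: at low noise the error is late. A reader might also infer that the trial has no usable measure of duration. It does, because phone-reported duration is already planned in 14.3. The defect is an undefined event and two unreconciled measures.

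**Conclusion.** The point holds as a should-fix. Read as first return to a single baseline score, with sampling stopped at reported loss, the planned median does not reliably measure duration of benefit. At effect 6.6 and SD of change 10 down to 5, it lies anywhere from about 13 to 26 weeks for the same true duration. That is a spread of 13 weeks against a 2.4-week target.

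The direction is not fixed: early at high noise, late at low noise (at SD 3.6 early crossing is only about 8 to 11%). The sizes rest on the first-crossing rule, an abrupt loss of effect, normal durations, and a noise SD that the documents do not give. The mismatch between event and end of sampling, and the lack of a governing measure, need none of these assumptions beyond reading loss of benefit as patient-judged.

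**What to change.** In 5.2, 14.3, 14.4 and 14.6, name one governing duration event: the first report that the desired effect is lost, from item 4 of 9.6. In the analysis:
- count laryngeal toxin re-injection as an event (an analysis rule only; the withdrawal rule in section 13 is not touched);
- give duration zero to subjects who report no benefit at any contact;
- treat the event time as interval-censored between contacts.

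Keep VHI-10 over time as a supportive profile. If a VHI-10 return time is also kept, define it with a margin or a confirmation rule, and collect VHI-10 to a fixed end of follow-up regardless of reported loss. That end must be named, because 4.1 gives 36 weeks while six monthly visits end at about week 26.

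**Cost.** The main change is wording, since the item is already collected. Continued VHI-10 adds some remote questionnaires and would need 5.2, 9.6 and Appendix 1 changed. If each comes as a full set of questionnaires and voice recording, screening, day 14 and six monthly entries at $10 come to 8 × 10 = $80, below the $150 cap in 9.6. The downside is that the main duration measure rests on open-label self-report, as the phone-call measure in 14.3 already does.
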